8.3.3 Orotic Acid Excretion

The excretion of orotic acid will be determined over a 24-hour period. Urine samples will be collected approximately every 6 hours ($\times 4$) at Baseline (Day 0) and over time to Week 52 after administration of DTX301 (Table 15-1). Details for the preparation and shipment of samples are included in the laboratory manual.

8.4 Quality-of-Life Assessment

8.4.1 PROMIS Questionnaire

Subjects will be asked to complete the Patient-Reported Outcomes Measurement Information System (PROMIS) questionnaire (Appendix 15.2.1) on Day 0 (predose) and then at Weeks 6, 12, 24, and 52 during the study (Table 15-1). **NOTE:** The PROMIS questionnaire should be completed prior to the neuropsychological tests on Day 0 and at Week 52.

Patient-reported outcomes will be assessed by components of the PROMIS questionnaire, an instrument developed in collaboration with National Institutes of Health, which has been designed, calibrated, and validated using a large sample size of participants with chronic diseases for use in clinical care and research. PROMIS measures may be used as endpoints in clinical studies to assess the effectiveness of treatment. The UCD Consortium also uses the PROMIS questionnaire for the evaluation of QoL in their Longitudinal Study participants.

Domains measured by PROMIS include physical, mental, and social well-being; versions of the PROMIS instrument include ones specific for adult and pediatric populations as well as for parent-proxy reporting for pediatric patients. The adult versions for the following self-reported domains will be included in this study [Reeve 2007; PROMIS 2009]: Cognitive Function, Anxiety, Depression, and Emotional/Behavioral Dyscontrol.

8.5 Neuropsychological Tests

All neuropsychological tests will be administered to English speaking subjects (at a minimum) in a nonfasted state. All neuropsychological tests are to be administered by appropriately qualified individuals as determined by sponsor or representative. The subject's plasma ammonia level should be $< 100 \mu\text{mol/L}$ (Section 8.2.4.1) or within the range of historical ammonia levels obtained when the subject was clinically stable (Section 4.1) in order to perform the neuropsychological tests. If the ammonia level is inconsistent with the subject's clinical status, the ammonia level may be repeated to ensure accurate results. The study site may use the time 0 (T 0) plasma ammonia sample (from

Protocol: 301OTC01

AUC₀₋₂₄ plasma ammonia) analyzed by the local laboratory (STAT sample) to determine the subject's plasma ammonia level. The result must be available prior to initiating the tests. If the subject is deemed clinically unstable, the neuropsychological tests will be held until the subject is determined to be clinically stable. Subjects may request pauses to rest during administration of the neuropsychological test battery, but the entire battery should be completed in 1 session. Additional details are provided in the neuropsychological section of the manual of operations.

The neuropsychological assessments have been selected in close consultation with [name] and are based on assessments where OTC participants in the UCD Consortium Longitudinal Study have shown cognitive deficits thus far (refer to the neuropsychological section of the manual of operations for further details). The most informative neuropsychological tests, as determined by these Phase 1/2 study data, may be included in further clinical studies with DTX301.

Neuropsychological deficits, especially in memory and executive functioning, are considered to be important aspects of the OTC deficiency condition and have widespread effects on daily functioning and relationships. Improving or normalizing plasma ammonia and other blood biomarkers (glutamate and glutamine) is hypothesized to potentially improve neuropsychological functioning. Therefore, it is important to establish neuropsychological functioning prior to dosing with DTX301 as well as evaluate the trajectory of this functioning longitudinally, ideally over several years. During the 4-year extension study, subjects will take this same neuropsychological battery of tests every 2 years to assess changes over time in motor, executive, and memory function.

8.5.1 Intelligence

Subjects will be asked to complete the Vocabulary and Matrix Reasoning subtests from the Wechsler Abbreviated Scale of Intelligence, Second Edition (WASI-II) at Baseline only (Table 15-1). The WASI-II provides general measure of cognitive function in subjects aged 6 to 89 years. The Vocabulary and Matrix Reasoning subtests provides an accurate, validated assessment of IQ that is highly correlated ($r=0.86$) with results from the Wechsler Adult Intelligence Scale, Fourth Edition (WAIS-IV) [Wechsler 2011]. The estimated time needed for completion of the WASI-II is 30 minutes.

Protocol: 301OTC01

8.5.2 Motor Function

8.5.2.1

[REDACTED]

8.5.3 Executive Function

8.5.3.1

[REDACTED]

8.5.4 Memory

8.5.4.1

[REDACTED]

8.6 Genotyping

8.6.1 Ornithine Transcarbamylase Genotyping

At Baseline, subjects will be asked to provide a single whole-blood sample for OTC genotyping. The objective of this research is to provide a background understanding to the etiology of the subject's OTC deficiency and to investigate any relationship between genetic factors and the subject's response to DTX301. The results do not need to be available prior to dosing with DTX301.

8.7 Other Assessments

8.7.1 Demographic, Medical, and Ornithine Transcarbamylase Deficiency History Assessments

As allowed by local laws and regulations, the following demographic data may be captured on the appropriate page in the eCRF: date of birth, sex, race, and ethnicity.

Medical, medication, and OTC deficiency medical history will be assessed as related to the eligibility criteria listed in Section 4.1 and Section 4.2.

8.7.2 Ammonia Scavenger Use and Dietary Protein Intake

The use of ammonia scavenger therapy and dietary protein intake will be reviewed and recorded at each visit (Table 15-1).

Changes to baseline treatment cannot occur until there is evidence of transgene expression reflected by continued evidence of metabolic stability with ammonia levels in the normal range or improved ammonia control if subjects have a history of ammonia levels above the upper limit of normal and supported by improvement in clinical signs and symptoms. The subject must be clinically stable and under good metabolic control before changes can be initiated or progressed. The risks of making adjustments to baseline treatment on their own, without express guidance from the site, will be reinforced with the subject at site visits.

Changes to baseline treatment cannot occur while the subject is treated with corticosteroids or within a 2-week period of completing a corticosteroid taper.

Protocol: 301OTC01

Tapering or discontinuation of ammonia scavenger therapy cannot occur at the same time and/or visit as modification of protein-restricted diet. At any time after modification and/or discontinuation of ammonia scavenger therapy, reinstatement of therapy may take place based on the subject's clinical and metabolic status (elevated ammonia levels, or signs and symptoms consistent with hyperammonemia), and under evaluation of the investigator.

Subjects will receive a prescribed diet (grams of protein per 24 hours) on Day 0 of the study and this diet will be reviewed at Weeks 6, 12, 24 and 52. Dietary protein intake by the subject between visits and dietary restrictions will be reviewed at each visit (Table 15-1) and recorded in the source documentation. **Modification of baseline protein-restricted diet cannot occur at the same time and/or visit as modification of baseline ammonia scavenger therapy.** At any time after protein-restricted diet has been modified or fully liberalized, reinstatement of restrictions may take place based on the subject's clinical and metabolic status and under evaluation of the investigator.

Once medications or diet are adjusted or discontinued, the subject must demonstrate good metabolic control prior to adjustments in the other type of baseline treatment.

9 Safety Monitoring and Reporting

9.1 Adverse Events and Serious Adverse Events

Adverse events will be assessed from the time the subject signs the ICF through the end of study/early withdrawal visit.

At every study visit, subjects will be asked a standard nonleading question to elicit any medically related changes in their well-being.

In addition to subject observations, AEs identified from any study data (eg, laboratory values, physical examination findings, ECG changes) or identified from review of other documents (eg, subject diaries) that are relevant to subject safety will be documented on the AE page in the eCRF.

9.1.1 Definitions

9.1.1.1 Adverse Events

The investigator is responsible for reporting all AEs that are observed or reported during the study, regardless of their relationship to study product or their clinical significance.

Protocol: 301OTC01

An AE is defined as any untoward medical occurrence in a subject enrolled into this study regardless of its causal relationship to study product. Subjects will be instructed to contact the investigator at any time after the subject signs the informed consent if any signs or symptoms develop.

A treatment-emergent AE is defined as any event not present before exposure to study product or any event already present that worsens in either intensity or frequency after exposure to study product.

9.1.1.2 Serious Adverse Events

An SAE is defined as any event that:

- Results in death
- Is immediately life-threatening
- Requires inpatient hospitalization or prolongation of existing hospitalization.
 - **NOTE:** Hospitalization due to hyperammonemic crisis (HAC [Section 3.2.6]) will be considered an SAE.
 - **NOTE:** Nonemergent hospitalizations for subject monitoring in the setting of steroid administration for vector-induced hepatitis (Section 8.2.4.1.2) will not be considered an SAE.
- Results in persistent or significant disability/incapacity
- Results in a congenital anomaly/birth defect

Additionally, important medical events that may not result in death, be life threatening, or require hospitalization may be considered SAEs when, based upon appropriate medical judgment, they may jeopardize the subject or may require medical or surgical intervention to prevent one of the outcomes listed in this definition. Examples of such medical events include allergic bronchospasm requiring intensive treatment in an emergency room or at home, blood dyscrasias or convulsions that do not result in inpatient hospitalization, or the development of drug dependency or drug abuse.

9.1.2 Safety Reporting

9.1.2.1 Adverse Events

All AEs reported or observed during the study will be recorded on the AE page in the eCRF. Information to be collected includes drug treatment, dose, event term, time of onset, investigator-specified assessment of severity and relationship to study product, corticosteroid

Protocol: 301OTC01

regimen, [1-¹³C] sodium acetate, OTC deficiency, or hyperammonemia, time of resolution of the event, seriousness, any required treatment or evaluations, and outcome. Adverse events resulting from concurrent illnesses, reactions to concurrent illnesses, reactions to concurrent medications, or progression of disease states must also be reported. All AEs will be followed to adequate resolution. The Medical Dictionary for Regulatory Activities (MedDRA) will be used to code all AEs.

Any medical condition that is present at the time that the subject is screened but does not deteriorate should not be reported as an AE. However, if the condition deteriorates at any time during the study, it should be recorded as an AE.

9.1.2.2 Serious Adverse Events

Any AE that meets SAE criteria (Section 9.1.1.2) or any of the safety stopping criteria (Section 3.2.7) must be reported by the study site to PPD Pharmacovigilance (PVG) Department immediately (ie, within 24 hours) after the time study site personnel first learn about the event. The study site should record all SAE information in the SAE eCRF and submit the report via the electronic data capture (EDC) system. An event meeting any of the safety stopping criteria should only be reported as an SAE in the EDC system if it meets SAE criteria (Section 9.1.1.2).

In the event of any fatal or life-threatening SAE, the investigator must immediately inform PPD PVG by telephone (Table 9-1) and report the SAE in the EDC system. If, for any reason, it is not possible to report the SAE in the EDC system (eg, the EDC system is unavailable), the study site should record the SAE on the paper SAE Reporting Form and fax it to PPD PVG (Table 9-1). As soon as it is possible, any SAE reported via fax must be entered into the EDC system.

Table 9-1 PPD PVG Contact Information for SAE Reporting

| Region | Contact Information |
|---------------|--------------------------------------|
| Rest of World | Safety hotline: [REDACTED] |
| | Safety fax ^a : [REDACTED] |
| North America | Safety hotline: [REDACTED] |
| | Safety fax ^a : [REDACTED] |

Abbreviations: PVG, pharmacovigilance; SAE, serious adverse event.

a. This is the preferred fax number for all regions. The toll-free fax number for North America can be provided upon request.

9.1.2.2.1 Expedited Reporting

The sponsor is responsible for reporting serious, unexpected, suspected adverse drug reactions (SUSARs) involving the study product(s) to all regulatory authorities and participating investigators in accordance with International Council for Harmonisation (ICH) guidelines and/or local regulatory requirements, as applicable. It is the responsibility of the investigator or designee to promptly notify the local institutional review board (IRB)/independent ethics committee (IEC)/institutional biosafety committee (IBC) of all SUSARs involving risk to human subjects.

As there is no prior clinical experience with DTX301, reference safety information for assessing whether an AE is a SUSAR is currently not available. Therefore, any SAE considered related to DTX301 will be considered a SUSAR and reported immediately as detailed in Section 9.1.2. The SAE should be treated with appropriate supportive and medical care deemed necessary for the well-being of the subject.

9.1.3 Assessment of Severity/Toxicity

The severity/toxicity, or intensity, of an AE refers to the extent to which an AE affects the subject's daily activities. The intensity of the AE will be rated as Grade 1, 2, 3, 4, or 5 using the most current version of the National Cancer Institute (NCI) CTCAE [NCI CTCAE 2018]. The CTCAE provides descriptive terminology that can be used to standardize AE reporting. A severity/toxicity grade is provided for each AE term that is grouped by the highest level of MedDRA classification [NCI CTCAE 2018]. Specific symptoms and medical conditions have a clinical description for each level of severity/toxicity. In the event that an AE occurs during the study that is not captured by the CTCAE, the AE should be graded according to the general guidelines outlined in Table 9-2.

Table 9-2 General Guidelines for Grading Events not Captured by the CTCAE

| Grade | Criteria |
|----------|--------------------------------------------------------------------------------------------------------------------------------------------------------------------------------------|
| Grade 1: | Mild; asymptomatic or mild symptoms; clinical or diagnostic observations only; intervention not indicated. |
| Grade 2: | Moderate; minimal, local, or noninvasive intervention indicated; limiting age-appropriate instrumental ADL ^a . |
| Grade 3: | Severe or medically significant but not immediately life-threatening; hospitalization or prolongation of hospitalization indicated; disabling; limiting self-care ADL ^b . |
| Grade 4: | Life-threatening consequences; urgent intervention indicated. |
| Grade 5: | Death related to AE. |

Abbreviations: ADL, activities of daily living; AE, adverse event.

- a. Instrumental ADL refers to preparing meals, shopping for groceries or clothes, using the telephone, managing money, etc.
- b. Self-care ADL refers to bathing, dressing and undressing, feeding self, using the toilet, taking medications, and not bedridden.

Changes in the severity/toxicity of an AE should be documented to allow an assessment of the duration of the event at each level of intensity to be performed. Adverse events characterized as intermittent do not require documentation of onset and duration of each episode.

9.1.4 Assessment of Causality

The investigator’s assessment of an AE’s relationship to study product is part of the documentation process, but it is not a factor in determining what is or is not reported in the study. If there is any doubt as to whether a clinical observation is an AE, the event should be reported.

Protocol: 301OTC01

The relationship or association of the study product in causing or contributing to the AE will be characterized using the following classification and criteria:

- Unrelated:** This relationship suggests that there is no association between the study product and the reported event.
- Possible:** This relationship suggests that treatment with the study product is causing or contributing to the AE; ie, the event follows a reasonable temporal sequence from the time of the study product administration or follows a known response pattern to the study product but could also be produced by other factors.
- Probable:** This relationship suggests that a reasonable temporal sequence of the event with the study product administration exists and, based upon the known pharmacological action of the study product, known or previously reported adverse reactions to the drug or class of drugs, or judgment based on the investigator's clinical experience, the association of the event with the study product seems likely. The event disappears or decreases on cessation or reduction of the dose of study product.
- Definite:** This relationship suggests that a definite causal relationship exists between the study product administration and the AE, and other conditions (concurrent illness, progression/expression of disease state, or concurrent medication reaction) do not appear to explain the event. The event reappears or worsens if the study product is re-administered.

The relationship or association of corticosteroid regimen, [1-¹³C] sodium acetate, OTC deficiency, or hyperammonemia in causing or contributing to the AE will also be characterized using the classification terms above.

9.1.5 Follow-Up of Subjects Reporting Adverse Events

All AEs must be reported in detail on the appropriate page in the eCRF and followed to satisfactory resolution, until the investigator deems the event to be chronic or not clinically significant, or until the subject is considered to be stable.

9.2 Procedures for Handling Special Situations

9.2.1 Pregnancy

A serum pregnancy test will be performed on all female study subjects of childbearing potential during Screening. A urine pregnancy test will be performed on all female study subjects of childbearing potential at each visit specified in the Schedule of Events ([Table 15-1](#)).

Protocol: 301OTC01

Pregnancy is not regarded as an AE unless there is a suspicion that a study drug may have interfered with the effectiveness of a contraceptive medication. Any pregnancy in a female study subject that occurs during study participation must be reported using the paper Pregnancy Report Form and fax it to PPD PVG (Table 9-1). To ensure subject safety, each pregnancy in a female study subject must be reported to PPD PVG Department (contact information in Section 9.1.2.2) within 2 weeks of learning of its occurrence.

The pregnancy in a female study subject must be followed up to determine outcome (including spontaneous miscarriage, elective termination, normal birth, or congenital abnormality) and status of mother and child, even if the subject discontinued from the study. Pregnancy complications and elective terminations for medical reasons should not be reported as an AE or SAE. Spontaneous miscarriages must be reported as an SAE. All neonatal deaths that occur within 28 days of birth should be reported as an SAE.

Any SAE occurring in association with a pregnancy in a female study subject brought to the investigator's attention after the subject has completed the study and considered by the investigator as possibly related to the study product, must be promptly reported to Ultragenyx Pharmaceutical.

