Symptomatic hyperammonemic events, classified as hyperammonemic crises (HAC) are often triggered by acute stressors, most commonly concurrent infection, but can become a life-threatening event at any age [Lichter-Konecki 2013; Batshaw 2014]. For example, adults with late-onset OTC deficiency have become hyperammonemic after crush injury, following surgery, when on a high-protein diet, during the postpartum period, and when treated with chemotherapy, high-dose corticosteroids, valproate, or haloperidol [Lichter-Konecki 2013; Batshaw 2014]. Consistent with the Urea Cycle Disorders Consortium (UCDC), we have defined hyperammonemic crisis (HAC) in this study as an episode of signs and symptoms associated with hyperammonemia (such as frequent vomiting, nausea, headache, lethargy, irritability, combativeness, and somnolence), with documented elevated ammonia levels (≥ 100 $\mu\text{mol/L}$) and requiring medical intervention [Kent and Holt 2017; Longo and Holt 2017; Diaz 2019].

Successful rescue from an initial hyperammonemic crisis does not eliminate the chronic risk patients have for developing repeat episodes of hyperammonemia, which may present as lethargy, seizures, or coma. Regardless of the age of onset, neuropsychological complications for all individuals with OTC

Protocol: 301OTC01

deficiency typically include developmental delay, learning disabilities, intellectual disability, attention deficit hyperactivity disorder, and executive function deficits.

The current standard of care for OTC deficiency is to limit dietary protein intake and supplement the diet with a high-energy source, such as glucose [Leonard 2001]. If plasma ammonia is not stabilized by dietary restriction alone, ammonia scavengers that promote an alternative pathway of nitrogen removal can be administered [Batshaw 2001; Häberle 2012; Lichter-Konecki 2013; Häberle 2019]. Ammonia scavengers cannot, however, completely prevent individuals from having hyperammonemic crises [Batshaw 2001]. Orthotopic liver transplantation can correct OTC deficiency; however, this is limited by donor availability and is associated with significant risk of morbidity and mortality [Leonard 2004].

Thus, there remains a significant unmet medical need for a treatment that allows for sustained ammonia management and prevention of hyperammonemic crises associated with OTC deficiency.

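### Protocol 9.2.1 tells sites not to report pregnancy complications as AEs or SAEs, which contradicts the protocol's own AE and SAE definitions

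*Protocol*

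**What the plan says.** Protocol 9.2.1 sets the pregnancy rules. A pregnancy goes on a paper Pregnancy Report Form to the pharmacovigilance department within 2 weeks of the site learning of it, and is followed to its outcome. The section then instructs: "Pregnancy complications and elective terminations for medical reasons should not be reported as an AE or SAE". The next two sentences make spontaneous miscarriage, and neonatal death within 28 days of birth, reportable as SAEs. The next paragraph requires prompt reporting of a possibly related SAE associated with a pregnancy that comes to light after the subject has completed the study.

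The general rules are in 9.1.1. Section 9.1.1.1 says "An AE is defined as any untoward medical occurrence in a subject enrolled into this study regardless of its causal relationship to study product" and makes the investigator "responsible for reporting all AEs that are observed or reported during the study". Section 9.1.1.2 lists the SAE criteria, among them "Requires inpatient hospitalization or prolongation of existing hospitalization" and "Results in a congenital anomaly/birth defect", and adds a clause for important medical events. It also says that hospitalization for hyperammonemic crisis "will be considered an SAE". Section 9.1.4 tells sites to report when they are unsure whether something is an AE. Section 10.2 makes the incidence of AEs, treatment-emergent AEs and SAEs the primary endpoint.

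**The concern.** A site with a pregnant subject who develops a complication finds two opposite instructions in one chapter. The general definitions require the event to be reported, and the specific pregnancy rule forbids it. A site may reasonably treat the specific rule as the governing one.

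AE and SAE incidence is what this study primarily measures, so an event kept off those pages is lost to the primary endpoint. SAE status also drives the 24-hour report in 9.1.2.2 and the SUSAR handling of related SAEs in 9.1.2.2.1. The DLT definition in 10.5.1 is likewise built on AEs and SAEs. Pregnancy is a foreseen possibility: women of childbearing potential may enroll, and urine pregnancy tests are scheduled through Week 52.

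**Working it through.** The plan states no figure on this point, so the check sets the rules side by side.

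1. **Is there an exception for pregnancy in the general rules?** No. Section 9.1.1.1 has none. The one hospitalization carve-out in 9.1.1.2 covers nonemergent monitoring stays during steroid treatment for vector-induced hepatitis. The exemptions in 8.2.4 and 9.1.2.1 concern OTC-related findings and conditions already present at screening.

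2. **Does 9.2.1 limit itself by seriousness or relatedness?** No. As worded, it covers a mild complication and a life-threatening, product-related one alike. Compare the overdose rule in 9.2.2.1: an overdose without symptoms need not be an AE, but any AE associated with it must be reported.

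3. **Case by case:**

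| Event | Under 9.1.1.1 and 9.1.1.2 | Under 9.2.1 | Conflict |
|---|---|---|---|
| Complication, not serious | AE | Not reported | Yes |
| Complication, hospitalized or life-threatening | SAE | Not reported | Yes |
| Termination for medical reasons | Not a listed SAE criterion in itself; its medical reason, an admission or the important-event clause may qualify | Not reported | Through the underlying reason |
| Miscarriage, neonatal death | Reportable | SAE | No, but the adjacent rule goes the other way |
| Congenital anomaly | SAE criterion | Followed as an outcome; not named in the disputed sentence | No |
| Hospitalized hyperammonemic crisis in pregnancy or postpartum | SAE | Not named; affected only if a site calls it a pregnancy complication | Ambiguity only |

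On the last row, the protocol Introduction lists the postpartum period among the settings in which adults with this disease have become hyperammonemic ("following surgery, when on a high-protein diet, during the postpartum period"). The question could therefore arise in practice.

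4. **Is there a route back into the analysis?** SAP 9.1 repeats the broad AE definition and has no step that brings in events recorded only on a Pregnancy Report Form.

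5. **What else captures such an event?** Protocol 3.2.7 requires 24-hour reporting of a death or an event of Grade 3 or higher. For events the CTCAE does not cover, 9.1.3 counts an indicated hospitalization as Grade 3. A severe complication is therefore reached by the wording of 3.2.7. The cover is partial: 9.1.2.2 applies its 24-hour route to an AE meeting the criteria, and enters such an event as an SAE only if it is one. That leads back to the conflict with 9.2.1. Events below Grade 3 have no such cover.

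6. **Expected number of affected events.** This would need a pregnancy rate and a complication rate. The documents give neither, so no number is computed.

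**The case against.** The strongest reply is that the sentence is untidy but does little harm. Pregnancy is excluded at entry, contraception is required for 52 weeks, and enrollment is at most 18. Severe events fall under 3.2.7. The Pregnancy Report Form goes to the same pharmacovigilance department. Section 9.1.4 favours reporting in doubt. SAP 3.1 records that Cohort 4 enrollment ended after 2 patients, so new wording may change little in this trial. The neighbouring sentences also suggest that the word not may be a drafting slip, though the documents do not establish this.

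Most of this stands, and it limits the size. It does not remove the contradiction: 9.1.4 deals with doubt, while 9.2.1 is an explicit instruction for a named class of events.

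A reader might infer more than the text supports:

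- **Reporting slips from 24 hours to 14 days.** The 2-week clock runs from learning of the pregnancy. No deadline is given for a later complication, so the comparison cannot be made.
- **Hyperammonemic crises drop out of the counts.** Crisis has its own definition (3.2.6), its own SAE rule and its own eCRF page (SAP 9.1).
- **Birth defects are no longer SAEs.** That criterion is untouched.
- **One missed SAE shifts a three-subject cohort by a third (1/3 = 33%).** That holds only if the subject has no other SAE, and it says nothing about how likely the event is.

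**Conclusion.** The contradiction is real and lies in an operative reporting rule. Section 9.2.1 bars events that 9.1.1.1 and 9.1.1.2 require sites to report, sits against the default in 9.1.4, and does not fit the sentences around it. The consequence is conditional: a pregnancy must occur on study, a complication or medically indicated termination must follow, and the site must obey 9.2.1 rather than the general definitions. The qualifying event would then be absent from the primary endpoint and the SAE-based reporting route, apart from the partial cover in 3.2.7. Few such events are expected and no rate is given, so no numerical magnitude is claimed. Nothing in the documents shows that any event has actually been left out. The point should be corrected because it concerns how the primary endpoint is ascertained and is inexpensive to repair.

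**What to change.** Reconcile 9.2.1 with 9.1.1.1 and 9.1.1.2 in three parts:

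- Replace the sentence so that pregnancy complications, and the medical reasons for terminations, are recorded as AEs, and as SAEs when they meet 9.1.1.2, in addition to the Pregnancy Report Form.
- State that hospitalization for hyperammonemic crisis remains an SAE during pregnancy and postpartum.
- Before analysis, check every existing Pregnancy Report Form against the AE/SAE database and add any event that was left off.

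The cost is a small protocol amendment, with the ethics and biosafety committee approval that 13.2.1 requires, and a short data reconciliation. The existing AE and SAE pages suffice. With Cohort 4 closed to enrollment, the reconciliation is the part most likely to matter for this trial's own results.
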